1.2 Schema

Figure 1: Overall Study Schematic

Screening (Day -90 to Day -2)	Day -2	Day -1	Day 1	Day 2	Day 3	Day 4	Day 5	Day 6	Day 8-12	30 ±7 days and 90 ±7 days after last dose
Screening/Nutritionist Evaluations	Participant travel to be local to the NIH	Admission to NIH	Encaleret Therapy (Figure 2)					Discharge	Follow up labs and telephone contact	Follow up telephone contact
		Baseline Fasting labs	Safety and pharmacodynamic blood draws 4-8 times per day (Table B)							
		Daily 24-hour urine collection: Open Day -1 in AM Close Day 6 in AM								

PP = post-prandial

Figure 2: Treatment Schematic

	Screening (Day -180 to Day -2)	Day -2	Day -1	Day 1	Day 2	Day 3	Day 4	Day 5	Day 6	Follow up Lab and Telephone Contact	30-Day Telephone Contact	90-Day Telephone Contact
Encaleret				Encaleret every 12 hours								
Calcium	SOC Calcium								SOC Calcium			
			Calcium supplementation, individualized dosing									
			Dietary Calcium 1000 mg/day, adjusted as needed									
			Rescue Calcium PRN									
Calcitriol	SOC Calcitriol								SOC Calcitriol			
			Calcitriol if cCa <8.5 mg/dL									
			Rescue Calcitriol PRN									

SOC = Standard of care, BID = twice a day; TID = three times a day; PRN = as needed.

Rescue calcium and calcitriol and encaleret discontinuation per Table D.

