1.3 Schedule of Activities (SOA)

Table A Schedule of Activities

	Screening	NIH CC Inpatient Treatment Visit							Discharge	FU Lab ⁷	Lab Phone FU ⁸	30- Day Phone FU ⁹	90-Day Phone FU ¹⁰
		Admission		BID Dosing									
Days	-180 to -2	-2 OR -1	-1	1	2	3	4	5	6	8-12	9-15	30 ± 7	90 ± 7
Informed Consent	X												
Admission to clinic/ inpatient floor ¹	X	X											
Demographi cs, Medical history	X												
Eligibility assessment	X												
Height	X												
Weight	X		X					X					
Vital signs ²	X		X	X	X	X	X	X	X				
Physical examination	X		X					X					
Aes and SAEs, Prior/ Concomitant meds	X	X	X	X	X	X	X	X	X	X	X	X	
NPO at midnight for morning fasting labs; water and medications ok			X	X	X	X	X	X	X				
Encaleret 162 mg q12h				X	X	X	X	X					
Calcium Carbonate, individualize d dosages			X	X	X	X	X	X					
Nutritionist Visit	X												
Quantify dietary calcium intake			X	X	X	X	X	X					

Stop magnesium and potassium citrate (last doses on day -3)		X	X										
Stop activated vitamin D and baseline calcium supplements (last doses on day -2) ³			X										
Start calcitriol if cCa < 8.5 mg/dL ³						X	X	X					
Discharge, resume conventional therapy									X				
Telephone Contact											X	X	X
Screening Lab Tests ⁴	X												
Safety laboratory testing ⁵										X			
Evening mineral panel (Ca, Mg, PO ₄ , albumin)			X										
Blood β-HCG pregnancy test (WOCBP only)	X		X							X			
Blood Sampling ⁶			X	X	X	X	X	X					
24-hour Urine (Ca, Mg, PO ₄ , Cr, Na, K, Citrate, pH)	X		X	X	X	X	X	X					
Timed interval urine collections ⁷				X	X	X	X	X					
Renal Ultrasound	X												
ECG, 12-lead	X		X	X	X	X	X	X					

Abbreviations: Adverse Event = AE; Albumin = Alb; Electrocardiogram = ECG; BID = Twice daily; Blood Pressure = BP; Calcium = Ca; Chloride = Cl; Concomitant Medication = Con. Meds; Creatinine = Cr; Early Termination = (ET); End of Treatment = EoT.

Follow-up = FU; Heart Rate = HR; Lactate Dehydrogenase = LDH; Intact Parathyroid Hormone = iPTH; Magnesium = Mg; NPO = Nothing by mouth; National Institute of Health Clinical Center = NIH CC; Parathyroid Hormone = PTH; Phosphate = PO₄; Phosphorus = P; Potassium = K; Prothrombin Time/ Prothrombin Time = PT/INR; Red Blood Cell Count = RBC; Thromboplastin Time = PTT; Serious Adverse Event = SAE; Women of Childbearing Potential = WOCBP

¹ Participants may complete the Screening Visit as outpatients or be housed overnight at NIH CC.

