During this week-long inpatient study, hypoparathyroid participants on encaleret may experience fluctuations in their blood calcium levels including the potential for hypocalcemia and/or hypercalcemia. The long-term risk of such fluctuations with encaleret are not expected to be larger than the risk of current therapy, however it is possible such fluctuations may be more frequent during this proof-of-principle study. Notably, because these patients have insufficient functional parathyroid tissue, the risk for hypercalcemia is expected to be significantly less than the risk was in the previous studies of patients with ADH1 or premenopausal women. Similarly, hypophosphatemia that was induced by increased iPTH secretion in the previous study in patients with ADH1, is unlikely in this patient population. This study is designed to minimize the risk of untoward fluctuations in blood calcium and related serum chemistries: Participants will be supervised with frequent monitoring of blood calcium levels multiple times per day and may receive treatment for hypocalcemia or hypercalcemia, including oral or IV calcium and calcitriol as needed. To reduce the risk of symptomatic hypocalcemia or hypercalcemia, participants will be given a personalized robust calcium load based on their home calcium dosages and a starting dietary calcium of 1000 mg per day. Doses will be determined by an endocrinologist familiar with treating hypoparathyroidism and will be based on each participant's baseline requirements and blood calcium levels. Additional 'rescue' calcium and calcitriol will be added if the patients experience significant symptoms of hypocalcemia or an albumin-corrected blood calcium < 7 mg/dL (Table D). On day 3, if the albumin-corrected blood calcium continues to be persistently <8.5 mg/dL, calcitriol will be added at a dose determined by the investigators and based on the patient's pretreatment dosages and current blood calcium. Calcium and dietary calcium will be adjusted as needed by physician investigators trained in endocrinology.

Additional risks and potential discomforts related to the frequent blood and urine sampling procedures in the supervised setting of the inpatient stays are addressed in the Informed Consent Document and include medical history, physical examination, renal ultrasound, and

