6.1.2 Dosing and Administration

On Day -1/-2, participants who met eligibility criteria at the screening visit will be admitted to the NIH CC. Participants will not take their magnesium and potassium citrate starting on the morning of Day -2. Participants will not take their standard-of-care calcium or calcitriol starting on the morning of Day -1, and will instead start a personalized calcium supplementation, determined by investigators from their baseline calcium requirements and levels. They will start on a dietary daily calcium intake of approximately 1000 mg per day, which may be adjusted if needed.

Encaleret 162 mg twice a day will be administered to participants on Day 1 to 5. Additional calcium and/or calcitriol will be administered per algorithm (Table D) if required.

Calcium and calcitriol supplementation will be adjusted following the algorithm delineated in Table D with the primary goal of safety. Mild to moderate symptomatic hypocalcemia at any calcium level, cCa < 7 mg/dL, or borderline QT prolongation, would cause investigators to give oral calcium and/or calcitriol. Doses will be determined at the discretion of experienced investigator's understanding of the patient's prior supplement requirements and severity of hypocalcemia. IV calcium may be used for participants with severe hypocalcemic symptoms or QTcF > 500 ms. If a patient develops mild hypercalcemia, then calcium and calcitriol will be held until cCa is less than 9 mg/dL. If cCa has not trended down by 12 hours (or earlier per investigator discretion), encaleret will be stopped. If cCa is > 12 mg/dL, encaleret will be discontinued and calcium and calcitriol will be held until cCa is < 9 mg/dL, when home regimen is restarted.

On Day 3, investigators will add calcitriol supplementation if the albumin-corrected calcium remains < 8.5 mg/dL. The calcitriol dose will be determined by investigators, taking into account the current calcium level and the subject's baseline requirements.

The last dose of encaleret will be given on the night of Day 5. The patient will then resume calcium and calcitriol and be discharged home. If the patient is hypercalcaemic or hypocalcemic, their baseline calcium and calcitriol may be adjusted at discharge. If needed, they may remain at the NIH clinical center until their labs have stabilized to a safe level.

Table D: Titration algorithm:

		Encaleret Titration	Calcium supplementation titration*	Calcitriol titration*	Additional interventions/ monitoring

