Hypocalcemia	Severe symptomatic hypocalcemia (seizures, QTcF > 500)**	Continue encaleret	IV calcium until symptoms resolve, transition to oral calcium	Start or increase calcitriol	Monitor blood calcium every 4-6 hours until symptoms resolve
	Mild to moderate symptomatic hypocalcemia OR cCa < 7 mg/dL OR QTcF >480 OR Change in QTcF of >90 from baseline	Continue encaleret	Increase oral calcium and/or start or increase calcitriol		If QT prolonged, repeat ECG twice a day until QTc < 480 or <90 from baseline
	cCa 7-10.2 mg/dL without symptoms of hypo/hypercalcemia	Continue encaleret	Continue calcium	No change in dose until day 3. On day 3, if cCa remains < 8.5 mg/dL, start calcitriol.	
Hypercalcemia	cCa 10.2 – 12 mg/dL	Continue encaleret while holding calcium/calcitriol. Discontinue encaleret if cCa has not trended down up to 12 hours after holding calcium/calcitriol.	Hold calcium until cCa < 9 mg/dL, then restart calcium at a lower dose	Hold calcitriol if taking until cCa < 9 mg/dL, then consider restarting at a lower dose or discontinuing	
	cCa > 12 mg/dL	Discontinue encaleret	Hold calcium until safe to restart home regimen	Hold calcitriol until safe to restart home regimen	IV fluids, consideration of calcitonin therapy if hypercalcemia is prolonged

*This algorithm is meant as a guide and may not have considered all possible scenarios. Calcium and calcitriol titration will be determined by physician investigators specializing in endocrinology and will be based on the prior calcium/calcitriol dosage, the individual patient's prior response, and lab trends. Ultimate decisions regarding calcium and calcitriol changes will be made with the primary goal of patient safety even if this deviates from this algorithm.
 
**Note that severe hypocalcemia and hypercalcemia are not expected to occur during this study. Early intervention and close monitoring is in place to prevent these severe adverse outcomes from occurring.
 
cCa = Albumin-corrected blood calcium, QTcF = QT corrected using the Fridericia's correction equation, IV = intravenous
					

Drug Discontinuation

Encaleret will only be given at the 162 mg BID dosage during this study, but may be discontinued early in the setting of hypercalcemia per the algorithm in Table D.

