Day -2 or Day -1 (Admission): Participants will be admitted to the NIH CC either the day prior to dosing or two days prior to dosing based on subject convenience. All participants will be instructed to stop taking calcitriol and home calcium dosage, with last doses on Day -2. Participants on magnesium or potassium citrate will be instructed to stop these supplements, with last doses on Day -3. Calcium supplementation with calcium carbonate(500 mg elemental calcium) three times a day will start on Day -1. Baseline 24-hour urine will be opened the morning of Day -1, and fasting laboratory assessment will be obtained. Attempts will be made to collect fasting calcium levels prior to the morning calcium dosage, however, calcium will be given to participants if clinically indicated (for example, in the setting of hypocalcemia).

Days 1 to 5: Encaleret 162 mg BID will be taken orally by the patient. Detailed summary of planned calcium and calcitriol therapy is presented in Figure 2 and a dosing algorithm is presented in Table D. Frequent blood and urine sampling for 24-hours will be performed for safety and outcome measures (see [Table A and Table B](#)). Encaleret will be administered in the morning and evening with water approximately 12 hours between each dose. The last dose of study medication will occur on the evening of Day 5. Daily ECG will be performed for monitoring of QT interval.

Day 6 (Discharge): After the blood sampling is collected on the morning of Day 6 and the 24-hour urine is closed, all participants will resume their prior conventional treatment regimen. During Day 6, cCa levels will be monitored until the patient is discharged. This admission can be extended if additional monitoring or treatment (e.g., to stabilize calcium) is needed prior to discharge.

Follow-up:

Outpatient testing done on day 8-12 (Less than 7 days after expected discharge from the NIH clinical center) will be collected either at the NIH CC or local laboratory. Blood samples collected will be evaluated for blood creatinine, albumin, calcium, magnesium, phosphate, and PTH. A telephone contact to the patient will be conducted once calcium results are available to be reviewed with investigative team. Additional outpatient testing to follow up safety issues will be performed as needed.

An additional two telephone contacts will be performed at 30-days (\pm 7 days) and 90-days (\pm 7 days) after the last encaleret dose for screening of AEs and pregnancies, respectively.

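### Section 8.2 orders a fixed 1500 mg/day of supplemental calcium from Day -1, while Sections 6.1.2 and 2.3.1, Figure 2 and Table A order an individualized dose of unstated amount

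*Combined protocol and SAP*

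**What the plan says.** Home therapy ends just before the inpatient baseline day. Section 8.2 states: "All participants will be instructed to stop taking calcitriol and home calcium dosage, with last doses on Day -2". What replaces the home calcium is described in two ways.

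**Fixed.** Section 8.2, in the admission paragraph: "Calcium supplementation with calcium carbonate(500 mg elemental calcium) three times a day will start on Day -1". It carries no participant-specific qualifier.

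**Individualized.**
- Section 6.1.2: from the morning of Day -1 participants "will instead start a personalized calcium supplementation, determined by investigators from their baseline calcium requirements and levels".
- Section 2.3.1: "participants will be given a personalized robust calcium load based on their home calcium dosages".
- Section 1.2, Figure 2: "Calcium supplementation, individualized dosing".
- Section 1.3, Table A: a calcium carbonate row, marked from Day -1 to Day 5, also labelled as individualized.

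For Days 1 to 5, Section 8.2 refers the reader elsewhere: "Detailed summary of planned calcium and calcitriol therapy is presented in Figure 2 and a dosing algorithm is presented in Table D". The footnote to Table D says that calcium and calcitriol titration "will be based on the prior calcium/calcitriol dosage, the individual patient's prior response, and lab trends".

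**The concern.** The two descriptions cover the same supplement from the same day. Unless a participant's personalized dose happens to be 1500 mg/day, following one text departs from the other, and Section 10.9.1 defines any departure from the approved protocol as a deviation.

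Two things are at stake. The first is safety wording. Section 2.3.1 presents the personalized load, together with dietary calcium, as a way to lower the risk of symptomatic hypo- or hypercalcemia. The text giving everyone the same dose does not describe that measure. The second is interpretation. This is a single-arm trial with at most 15 treated participants, and its secondary endpoint is built from blood calcium and 24-hour urine calcium. A reader of the results needs to know what calcium load lay behind those values, and the plan gives two answers.

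**Working it through.** **1. The fixed dose.** Section 8.2: 3 x 500 mg = 1500 mg/day of elemental calcium. With the dietary starting target of about 1000 mg/day (Section 6.1.2), the intended total is 1500 + 1000 = 2500 mg/day for every participant.

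**2. The individualized dose.** Call it P mg/day. No section gives P. Section 2.3.1 ties it to home dosages, Section 6.1.2 ties it to baseline requirements and levels, and Figure 2 and Table A name no basis. The difference between the two readings is 1500 - P. It is zero only when P = 1500, positive when P is smaller and negative when P is larger. Both its size and its sign are therefore open.

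**3. Is there a reconciling rule?** No section describes 500 mg three times a day as a default, a minimum or an example. Section 8.2 opens by deferring to the Schedule of Activities, whose Table A says individualized, and its Days 1 to 5 paragraph points to Figure 2, which says the same. Section 8.2 thus conflicts with the two sources it cites. Neither cross-reference states which text governs the Day -1 dose.

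**4. Does later titration settle it?** Table D tells investigators to continue calcium in participants without symptoms whose corrected calcium is 7-10.2 mg/dL, so the starting dose carries forward there by default. Its other rows, and its footnote, allow changes from whatever dose was started. None states the starting dose. Over the same days calcitriol is off unless given as rescue, or started on Day 3 for a corrected calcium still below 8.5 mg/dL (Section 6.1.2).

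**5. Which endpoint values are exposed?**

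| Endpoint (Section 3) | Values used | Starting calcium load |
|---|---|---|
| Secondary | Fasting blood calcium >8.5 mg/dL with 24-hour urine calcium <250 mg (women) or <300 mg (men), Days 1-5 | Direct: every value is taken on the study regimen |
| Primary, baseline | Fasting FECa, Day -1 | Largely none: Section 8.2 aims to draw the sample before the morning calcium dose |
| Primary, final | Fasting FECa, Day 6 or last on drug | Exposed, after up to five days of possible titration |

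The primary rows use the fasting definition in Sections 1.1, 3, 9.2 and 9.4.2. Section 9.1 describes FECa from 24-hour urine, which is a separate inconsistency. Section 8.2 also lets calcium be given before the sample when clinically indicated, so the baseline row is an intention rather than a guarantee.

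**6. Sample size.** Section 9.2 uses an SD of 20 percentage points and a two-sided 0.05 paired t-test. Power is P(T > t(0.975, n-1)), where T is noncentral t with n-1 degrees of freedom and noncentrality (change/20) x sqrt(n). Setting power to 80% gives detectable changes of 15.56% (n = 15), 19.92% (n = 10) and 33.64% (n = 5), which round to the plan's 16, 20 and 34. The calcium dose is not an input, so this calculation is unaffected.

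**The case against.** The best reply is that the consequence is limited. Calcium is measured several times a day, rescue is available, calcium can be given whenever clinically indicated, and the Table D footnote leaves changes to endocrinology investigators even where that departs from the algorithm. All of this applies under either reading. It stands as a limit on the safety consequence. It does not say what is ordered on Day -1.

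A second reply is that calcium intake varies under both readings: home calcium and calcitriol stop, diet may be adjusted, Table D changes doses, and calcitriol may start on Day 3. This also stands. A reader might infer that the contradiction is what mixes the encaleret effect with calcium intake, and that correcting it would separate them. The documents do not support that: individualized dosing itself gives participants different loads, and so does titration.

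Two further inferences go too far. One is that the primary and secondary endpoints are equally affected; the intended timing of the Day -1 fasting sample confines the primary-endpoint exposure to the on-treatment value. The other is a numerical gap, obtained by assuming home doses and an absorption fraction and setting the result beside the 250 and 300 mg urinary limits. The documents give neither quantity, no section equates the personalized dose with the home dose, and absorbed calcium is not the same as urinary calcium.

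**Conclusion.** The inconsistency is real and present in the current text: 1500 mg/day for all in Section 8.2, against an individualized dose of unstated amount in four other places. It is a conflicting instruction for a supplement that is actually administered, and it touches a stated safety measure, so it should be corrected. It bears directly on the secondary endpoint and, under the fasting definition, on the on-treatment FECa in the primary endpoint. The size of the effect on either endpoint cannot be computed from the documents, and no bias is demonstrated. The power calculation and the planned tests do not depend on it. Which regimen is appropriate is not judged here.

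**What to change.** - Reconcile Section 8.2 with Sections 6.1.2 and 2.3.1, Figure 2 and Table A so that one background calcium regimen is stated from Day -1. The sponsor decides which.
- State in the report which regimen already-treated participants received. Section 2.3.1 already describes the first 6 participants with PSH exposed to encaleret.
- List each participant's daily supplemental plus dietary calcium beside the FECa and 24-hour urine calcium results. This makes the load visible; it does not remove the variation in intake.

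The cost is a short protocol correction and one listing. No new data are needed: Section 6.5 has inpatient concomitant medications recorded, and Table A and the dietary calcium paragraph of Section 8 have daily dietary calcium assessed. Section 9.4.8 already allows individual data to be presented.

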8.2.1 Biospecimen Evaluations

Screening visit and inpatient blood samples except for research samples and PK samples will be managed by the NIH Clinical Center laboratory. Urine samples will be either managed by the NIH laboratory or sent to LabCorp. Only exploratory end points, for example FGF23, will

be performed in non-CLIA certified labs on research samples. The primary endpoint assessments include evaluations of urinary excretion of calcium. The times for collection of these samples are detailed in the Schedule of Activities in Section 1.3.

All PK blood samples will be analyzed by a CRO contracted by the manufacturer. Details for sample processing and handling will be provided in a written SOP. The times for collection of these samples are detailed in the Table B and C.

The total blood volume collected for each subject will be less than the blood volume limits per subject as per NIH Guidelines for Blood Draw Limits for Research Purposes (M95-9, June 2009). If a subject has a low body weight (<50 kg for adults), the blood volume taken will be reduced to remain within the NIH guidelines of 10.5mL/kg/8w.

In order to characterize both the pre-study calcemic status as well as changes associated with experimental interventions, the protocol will rely on frequent measurement of albumin-corrected blood calcium concentrations. Assays will be conducted according to specifications of the NIH Clinical Center Laboratory, Bethesda, MD. The main indicator of normal versus abnormal blood calcium levels will be based on the correction for serum or plasma albumin according to the formula corrected calcium (cCa) = measured total calcium (mg/dL) + 0.8(4 – albumin (g/dL)) OR measured total calcium (mmol/L) + 0.2(4 – albumin (g/dL)), recognizing that the total calcium reported in SI units (mmol/L) can be converted to conventional units (mg/dL) by multiplying by 4. Given that enrolled participants are expected to have both normal and stable albumin levels, the measures of total calcium and cCa are likely to be similar throughout the time course of this study. Ionized calcium assays will also be measured at the NIH Clinical Center and can be used to assess calcium status for dose adjustment decisions on a case by case basis in addition to the albumin corrected-calcium.

